## Statistical analysis

The comparison of clinical parameters between the two groups were conducted by the Student's t test, the Mann Whitney U-test, the Chi-square test or Fisher's exact test, relying on the variables as appropriate. The DFS and OS were determined by the Kaplan-Meier method which was generated by the log-rank test. The univariate and multivariate analyses were conducted to identify the independent risk factors of DFS and OS in the entire group of BCLC 0/A patients receiving operation in the recruitment period. Variables with P < 0.1 on univariable analysis were subjected to the multivariable Cox regression model using a forward stepwise variable selection. The statistical significance level was set at P < 0.05 in all the analyses.

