## Protocol

- 1. Adult patients diagnosed with hepatocellular carcinoma, suitable for partial hepatectomy were considered as potential candidates while the patients were referred to hospital (n=263).
- 2. In-hospital examination includes physical status, liver function and tumor stage. Patients with Child-Pugh A liver function, ECOG physical status 0/1, and BCLC stage 0/A were good candidates for surgical resection. These patients would be put forward to surgery and waiting for the postoperative pathological examination. Marginal resection was applied while tumor was adjacent to major vasculature or severe cirrhosis existed. We routinely mark the unsafe resection margin with silver clips for potential adjuvant postoperative therapy.
- 3. Once pathological examination proved micro-vascular invasion in paratumoral tissue, which meant a higher incidence of early recurrence for the patient, the patient would be considered as a candidate for enrollment.
- 4. The protocol and detail of the trial would be clearly explained to the patient and the written informed consent were collected if the patient agreed to be enrolled.
- 5. Randomization: Randomization was carried out using the random sequence method of EXCEL, keeping a 1:1 ratio in groups. Two nurses on daily duty accomplished the randomization and allocation work. Participants in SBRT group would be sent to a separate team of radiologists who carried out the radiotherapy and follow-up survey (n=76).
- 6. Concealment: Concealment was not attached in the SBRT group and blinding was not applied due to the SBRT procedure.
- 7. Surgery: The conventional open partial hepatectomy was applied in this study. After removal of the tumor, silver clips were imbedded to mark where resection

margin was narrow and absent. The marginal liver resection was defined as the minimal distance from tumor edge to the cut surface <5mm, regardless of the margin was positive or not.

- 8. Radiotherapy: SBRT was delivered by the CyberKnife® system (Accuracy Inc., Sunnyvale, CA, USA) with tumor tracking devices. All the patients received fiducial marker implantation in operation for the tumor tracking technique.
- 9. Follow-up: All the participants received follow-up every 3 months until recurrence or censored.

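### P-value screening followed by forward stepwise Cox selection tends to inflate weak to moderate hazard ratios and can drop the protocol's own reasons for marginal resection

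*SAP*

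**What the plan says.** The SAP, Statistical analysis, sets the aim: "The univariate and multivariate analyses were conducted to identify the independent risk factors of DFS and OS". The population is wider than the randomised set; the analysis is done "in the entire group of BCLC 0/A patients receiving operation in the recruitment period".

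The covariates are chosen in two rounds: "Variables with P < 0.1 on univariable analysis were subjected to the multivariable Cox regression model using a forward stepwise variable selection". The threshold for reading the result is common to everything: "The statistical significance level was set at P < 0.05 in all the analyses".

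The protocol (section Protocol, item 2) says why some patients have a narrow margin: "Marginal resection was applied while tumor was adjacent to major vasculature or severe cirrhosis existed".

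The text available for review gives no candidate list, no covariates that are always kept, no stepwise entry or removal thresholds, no shrinkage or internal validation, and no allowance for selection in the intervals or P values. The randomised comparison of DFS and OS is described separately, by Kaplan-Meier and log-rank.

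**The concern.** A variable of weak or moderate effect enters the final model mainly in those samples where its estimate happens to be large. The hazard ratio that is then reported tends to lie too far from 1, and the usual interval takes no account of how the variable got there.

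The rule also keeps a confounder only if it is itself significant. Item 2 gives vessel adjacency and severe cirrhosis as causes of marginal resection. If they also affect recurrence or survival, they confound the effect of margin. The regression covers all operated BCLC 0/A patients, so margin can vary there, and the protocol's Objectives link marginal resection to increased local recurrence. Margin is therefore a natural candidate.

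At stake is a risk-factor result that overstates modest effects, or that credits margin with an effect belonging to its indications. That error would mostly run in the direction of the trial's rationale.

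**Working it through.** The plan gives no sample size, event count or model-performance figure, so there is nothing of its own to reproduce.

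**Inputs from the documents.** Screen at P < 0.1; forward stepwise; P < 0.05; 263 potential candidates as an upper guide to the size of the regression set; 76 at the randomisation step as a small-sample case.

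**Assumed, because not given.** Two-sided tests; stepwise entry at P < 0.05; about 200 operated patients with about half having events; 12 candidates; binary factors.

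**1. Inflation, analytic check.** For a balanced binary factor, SE(log HR) ≈ 2/√events = 2/√100 = 0.20. Selection at P < 0.05 requires an estimate above 1.96 × 0.20 = 0.392. With β = ln(HR) and a = (0.392 − β)/0.20:

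- P(selected) = 1 − Φ(a)
- mean log HR when selected = β + 0.20 × φ(a)/P(selected)
- coverage when selected = 1 − 0.025/P(selected), because low-side misses are never selected for these β

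| True HR | β | a | P(selected) | Mean log HR | As HR | Coverage |
|---|---|---|---|---|---|---|
| 1.3 | 0.262 | 0.648 | 0.258 | 0.513 | 1.67 | 0.90 |
| 1.4 | 0.336 | 0.278 | 0.391 | 0.533 | 1.70 | 0.94 |
| 1.6 | 0.470 | −0.390 | 0.652 | 0.584 | 1.79 | 0.96 |

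**2. Inflation, simulation of the written rule** (1,200 runs):

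| True HR | HR when selected | Coverage | Full model HR | Full model coverage |
|---|---|---|---|---|
| 1.3 | 1.690 | 0.911 | 1.332 | 0.940 |
| 1.4 | 1.727 | 0.908 | 1.425 | 0.938 |
| 1.6 | 1.808 | 0.957 | 1.666 | 0.951 |

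**3. Sensitivity to covariate scale and events.** A second simulation used hazard ratios per SD, n = 263, 78 or 157 events and 12 or 20 candidates (300 runs per setting, Monte Carlo error up to about 6 points). Mean log HR when selected, relative to truth, was 1.34-1.92 for HR 1.2, 1.10-1.47 for 1.3, 1.01-1.26 for 1.4 and 1.01-1.12 for 1.6.

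The two sets agree once scale is matched. A balanced binary factor has SD 0.5, so a binary HR of 1.4 is √1.4 = 1.18 per SD. Its inflation in step 2, ln 1.727/ln 1.4 = 1.62, lies within the 1.34-1.92 found for HR 1.2 per SD.

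Coverage for truly prognostic selected factors was 0.94-0.96 with uncorrelated covariates and 0.91-0.94 at correlation 0.3. Over all selected variables, null ones included, it was 0.73-0.88, against 0.93-0.94 for the full model.

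**4. Margin and its indications.** Assumed: true margin HR 1.0; each indication HR 1.4-1.6; 30-50% events; marginal resection in 15% without an indication and 70-92% with one (1,500 runs). Stepwise called margin independent in 8.9-14.4% of runs, against 4.5-6.1% with both indications forced in. The margin HR when selected was 1.7-2.1. At least one indication was dropped in 73-96% of runs.

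A repeat with n = 200, both indications at HR 1.5 and each present in 30% of patients (600 runs per setting) gave 12.7% against 6.0% at 50% events, and 9.8% against 4.3% at 30% events.

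The excess is not universal. With a standardised confounder of HR 1.4 per SD, correlation 0.5 with a null exposure and n = 263, the exposure was selected in 5.3% (78 events) and 4.3% (157 events) of runs. A confounder that strong usually keeps itself in the model.

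**5. Noise only** (60% events, 1,500 runs). At least one false factor appeared in 32%, 47% and 59% of analyses for 8, 12 and 16 candidates. The formula 1 − 0.95^k gives 34%, 46% and 56%. A full model tested at P < 0.05 has a similar rate, so these figures describe multiplicity, not stepwise selection.

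**The case against.** The strongest reply has four parts.

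- **The confounding is only half documented.** Item 2 shows that cirrhosis and vessel adjacency lead to marginal resection. It does not say that they affect DFS or OS, and the SAP text names neither them nor margin as regression variables. This stands: the point has to be conditional. A reader might infer that known confounders have been dropped. The documents support only that nothing prevents it.
- **The sizes depend on invented inputs.** Events, candidates, prevalences and correlations are all assumed. Strong factors with many events show almost no inflation and near-nominal coverage, and negative confounding can bias a hazard ratio downward (1.28 for a true 1.40 in one setting with 157 events). This stands against any flat statement that the hazard ratios are too large and the intervals too narrow. It does not remove the tendency for weak to moderate factors, which the analytic check and both simulations show.
- **The analysis is secondary.** The stated objective is the efficacy of SBRT, compared by log-rank, and all randomised patients had marginal resection. This stands. It limits the reach of the point but does not answer it, because finding independent risk factors is a stated aim of the SAP.
- **The plan may say more.** Part of the SAP was not in the text available for review, so a covariate list cannot be excluded. Even with one, the selection rule as written would apply to it.

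A reader might also take the 32-59% noise-only rate as evidence against stepwise selection. It is not, since a full model shares it.

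**Conclusion.** The concern holds as a tendency in the secondary risk-factor analysis and should be put right. For weak to moderate factors, the rule tends to inflate the hazard ratios that survive: a true 1.3-1.4 is reported at about 1.7 on average, given binary factors and about 100 events. Under-coverage for such factors is modest, about 91% against 94% for the full model in the simulation. A true 1.6 is reported at about 1.8 with nominal coverage, and inflation shrinks further as events increase.

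The rule also leaves the two documented reasons for marginal resection unprotected. If both are prognostic with HR 1.4-1.6 and margin is a candidate, a null margin is named independent in about 9-14% of analyses instead of 5-6%. With a much stronger confounder the excess can vanish.

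A reader might infer that the trial's treatment result is compromised. The documents do not support this: the randomised DFS and OS comparison does not pass through the stepwise model.

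**What to change.** Replace the screening and stepwise sentence with one Cox model for DFS and one for OS:

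- Choose the covariates on clinical grounds, fix the list without reference to outcome P values, and size it to the events. About one covariate per 10 events is a workable guide. Size matters without selection too: at n = 76 with 45 events, full-model coverage fell to 0.91-0.92 with 12 variables and 0.87 with 20.
- Use no P-value selection.
- Where margin is a covariate, always include severe cirrhosis and major-vessel adjacency as recorded for the operated cohort.
- If the candidates exceed the events budget, use a penalised Cox model with bootstrap intervals.
- Report every hazard ratio with its 95% interval and label the analysis exploratory. A Holm adjustment for claims of a risk factor is an optional, separate multiplicity step.

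The documents are written in the past tense with counts, so if the data are already in hand, the report should say when the list was fixed.

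The cost is SAP wording and analysis time, with no new patients. Intervals will be wider and fewer factors will be declared significant. The documents do not show that both indications were coded for the whole operated cohort, so some extraction of already recorded operative data may be needed.
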